ENDPOINTS:

Primary Endpoint

- One point decrease from baseline in target lesion Global PG (GPG) Severity Score at Week 16

Secondary Endpoints

- Complete re-epithelization of PG lesions (GPG Severity Score of 0) at visits 3, 4, 5, 6, 7, 8, and 9.
- Absolute change from baseline in patient-reported pain severity (Pain-VAS) at visits 3, 4, 5, 6, 7, 8, and 9 and at complete re-epithelization of ulcer.
- Absolute change in quality of life (DLQI) from baseline at visits 3, 4, 5, 6, 7, 8, and 9 and at complete re-epithelization of ulcer.
- Recurrence of PG lesions after complete re-epithelization (GPG score 0) of all lesions and spesolimab cessation

- Time to worsening (1 or more GPG point increase) of target PG lesion from spesolimab cessation

STUDY DESIGN OVERVIEW:

This study is a prospective, proof-of-concept, open label clinical trial. The study will take place at Icahn School of Medicine at Mount Sinai.

The study will screen up to 25 subjects in order to enroll a total of up to 20 patients with at least one clinically measurable ulcerative PG lesion. Subjects will receive 900 mg of spesolimab intravenously (IV) over 90 minutes at a frequency of every 4 weeks until Week 28 with the following exceptions:

- At the Week 8 visit, subjects who do not show any improvement, show only minimal improvement, or those that begin to lose their initial improvement response (decrease in pain or wound drainage), may be switched to a dosing frequency of every 3 weeks through Week 26, at the discretion of the investigator. These subjects will still return at Week 16 for an endpoint visit, but will not receive treatment at this visit. Refer to Tables 3 and 4 for schedule of events.

All subjects will be monitored monthly for 4 months subsequent to treatment cessation.

Subjects who reach GPG score 0 at anytime during the study will continue to receive treatments until week 28 (or Week 26 depending on dosing frequency) and will then be monitored for 4 months subsequent to treatment cessation.

Subjects who are experiencing improvement in their PG but who have not reached complete wound healing will continue treatment until Week 28 (or Week 26 for those who were switched to every 3 week dosing), even if primary endpoint has been achieved. These subjects will then be monitored for 4 months subsequent to treatment cessation.

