During each treatment visit the subject will undergo clinical assessments (number, location, measurement of lesions, and GPG Score (Appendix 1)). Each visit will also consist of vitals, medication review, blood collection, patient PG questionnaire (wound dressings, pain VAS and DLQI (Appendix 2) and monitoring for adverse events. O-Link ® Inflammatory Serum Cytokine Panel, IL-1 β , and IL-36 subtype cytokine levels will be run from blood serum samples collected at Baseline/Week 0, Week 16, all follow-up visits, and/or at early termination visits. Blood samples for pharmacokinetics and antibody testing (Nab and ADA) will be collected at Baseline, Week 8, Week 16, Week 28 (or Week 26 depending on dosing frequency) and/or early termination visit. An extra 10mL aliquot of serum sample will be reserved for any additional exploratory serum testing done in the future.

PATIENT POPULATION:

Prior to enrollment, all subjects must meet the following inclusion and exclusion criteria:

Inclusion Criteria:

- 1) Male or female subjects \geq 18 years of age at the time of signing the informed consent document
- 2) Subject is able to understand and voluntarily sign an informed consent document prior to participation in any study assessments or procedures
- 3) Subject is able to adhere to the study visit schedule and other protocol requirements.
- 4) Subject has clinically diagnosed ulcerative PG with PARACELSUS score greater than or equal to 10 ⁽⁶⁾
- 5) Subject has at least one clinically measurable ulcerative PG lesion on his/her/their body that has failed to respond to at least one prior therapy such as (but not limited to) topical corticosteroids, intralesional triamcinolone, prednisone, cyclosporine, IL-23 inhibitor, IL-17 inhibitors, IL-1 inhibitors, or TNF- α blocker therapy
- 6) Subject has moderate to severe PG as determined by a GPG severity score of \geq 3
- 7) Subject is judged to be in otherwise good overall health as judged by the investigator, based on medical history, limited physical examination, and laboratory testing. (NOTE: The definition of good health means a subject does not have uncontrolled significant co-morbid conditions).

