Contraindications to spesolimab treatment include patients with severe or life-threatening hypersensitivity to spesolimab or to any of the excipients in spesolimab¹⁴. In our experience, patients infused with spesolimab exhibited no adverse reactions during or after treatment with no pre-medication required. There is limited data available on the impact of antidrug antibodies on safety and efficacy upon retreatment. Furthermore, it is not known whether spesolimab increases or decreases the efficacy of other medications.

PRIOR TREATMENT:

All relevant treatment received by the subject within 30 days before screening will be recorded.

CONCOMITANT TREATMENT:

Concomitant medications are permitted for the treatment of stable, chronic illness as well as for pyoderma gangrenosum. Concomitant treatments for pyoderma gangrenosum will tapered over spesolimab treatment course as tolerated. Use of such concomitant medication or other medications that may be required throughout the study will be recorded (including the reason for treatment and name, dose, unit, route, and the date of treatment as appropriate) until treatment termination and throughout follow-up period. Patients will be allowed to continue with biologic therapies used to treat comorbidities.

PROHIBITED TREATMENT:

All treatments prohibited by clinician during the screening period are also prohibited throughout the course of the study. No live attenuated vaccinations are permitted throughout the study.

PROCEDURES:

Monitoring of AEs will begin at the time of signing the informed consent form and will be continued throughout the course of the study. All study procedures will be completed at designated times during the study period (see Tables 3 and 4). Subjects will receive 900mg IV spesolimab at a frequency of every 4 weeks through Week 8, at which time, at the discretion of the investigator, dosing frequency may be increased to every 3 weeks. Subjects will continue to dose every 4 or 3 weeks through Week 28 or 26 (depending on

dosing frequency). Subjects will be monitored once a month, for 4 months after treatment cessation. Patients that, in the opinion of the investigator, are benefiting from treatment at week 28 but need more therapy to achieve wound closure may be eligible to continue on treatment (on case-by-case basis) to a maximum of 52 week after discussion with Boehringer Ingelheim trial team.

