Subjects are numbered sequentially. Each subject screened (total of 25 screened) will be assigned a unique screening number for the duration of the study. Subject screening numbers will also become a subjects treatment number if they are enrolled in the study after providing informed consent and meeting inclusion criteria. Subjects who discontinue or withdraw from the study before receiving a treatment assignment code, but re-enroll at a later time must be assigned a new screening number. The investigator must maintain a master log linking the subject number to the subject's name. The investigator must follow all applicable privacy laws in order to protect a subject's privacy and confidentiality.

INVESTIGATIONAL DRUG SUPPLY :

Eligible participants will receive 900 mg intravenous spesolimab starting at Visit 2/week 0/Baseline. All participants will receive a total of 8 or 9 infusions (depending on dosing frequency) through Week 28 or Week 26 (depending on whether the subject's dosing frequency is increased to every 3 weeks at Week 8), unless there is significant worsening. All subjects should be observed for 30 minutes following the infusion at Baseline to assess safety. Select cases will be offered the opportunity to continue treatment through Week 52 on case-by-case basis if the patient would benefit from continued treatment. All subjects who have not been discontinued will be monitored once a month, for 4 months after treatment cessation.

All study medication will be provided by Boehringer Ingelheim, refrigerated and stored between 2-8°C in a secure area. Study drug will be administered to subjects at each study visit in office. The investigative site will account for all study drug dispensed and stored during the study.

STATISTICAL CONSIDERATIONS:

Sample Size

This is a proof-of-concept, open-label trial. Twenty patients will be enrolled in the trial to demonstrate efficacy of spesolimab in a population of patients with moderate-severe, refractory PG. Although there is no formal power calculation, a sample size of n=20 subjects allows 81% power at 2.5% significance for a one-sided binomial test to detect at Week 16 a difference of 36.6% in the proportion of GPG success compared to a constant set to be equal to 10%. The choice of the constant was based on data from a randomized clinical trial for efficacy of infliximab where a group of 17 PG placebo-treated patients showed 6% response at Week 2 (Brooklyn et al.,2006).

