Demographics and Other Baseline Characteristics

Descriptive statistics of demographics and other baseline characteristics of patients will be summarized with mean, median, and standard deviation for quantitative outcomes, and frequency and percentage tables for categorical outcomes.. Other baseline characteristics include sex, age, height, weight, vital signs, duration of PG, history of pathergy or PG trigger (if known), concurrent diagnoses from medical history and indications for concomitant medication, concomitant medication, and previous PG treatments.

Target Lesion Measurement and Digital Image Assessments

Size of target PG lesion will be approximated at each visit by measuring the length, width and depth of the lesion. Target lesion will also be analyzed using Image J software to obtain a more precise surface area of each lesion using digital photographs taken at each visit.

Analysis of Primary Endpoint

We will compare the proportion of patients achieving one-point decrease in target lesion GPG score at Week 16 with a constant p=0.10. Clopper-Pearson 90% confidence interval will be estimated.

Analysis of Secondary Endpoints

- One sided Clopper-Pearson 90% confidence intervals will be estimated for the proportion of patients achieving re-epithelization (GPG Severity Score of 0) at Visits 3, 4, 5, 6, 7, 8, and 9
- We will apply a two-sided paired t-test to evaluate significance of the mean difference of GPG score at Week 16 versus Week 0.
- Mean patient reported scores of pain (Pain VAS) and quality of life (DLQI) at baseline will be compared to those at Week 16 and treatment termination using the student's t- test to compare between subject's pre and post-treatment scores.
- One sided Clopper-Pearson 90% confidence intervals will be estimated for the proportion of patients with recurrence or worsening of PG lesions from point of complete re-epithelization or spesolimab cessation at end of treatment visit (Week 28 or Week 26 depending on dosing frequency).

Interim Analysis

An interim analysis will be performed after the first 10 subjects complete Week 16. We will continue enrollment during this time. Proportion of patients achieving one-point GPG score decrease will be reported. Changes from baseline at Week 16 in the PG lesions (number, size, GPG score) will be evaluated and reported. Enrolled subjects will continue to receive treatments during this time.

Data Transfer and Management

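### The 10% null for Week 16 response rests on a Week 2 placebo figure from 17 patients, so rejecting it shows a rate above 10%, not efficacy at 2.5% error

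*Combined protocol and SAP*

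**What the plan says.** The Study Design Overview describes the design: "This study is a prospective, proof-of-concept, open label clinical trial". There is no control arm. Under Statistical Considerations, Sample Size, the purpose is stated as "Twenty patients will be enrolled in the trial to demonstrate efficacy of spesolimab". The same paragraph disclaims a formal power calculation but then says that "a sample size of n=20 subjects allows 81% power at 2.5% significance for a one-sided binomial test". The effect size attached to that power is 36.6%, and the comparator is a constant of 10%.

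One reason is given for that constant, namely that in a randomised infliximab trial "a group of 17 PG placebo-treated patients showed 6% response at Week 2".

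Analysis of Primary Endpoint then says "We will compare the proportion of patients achieving one-point decrease in target lesion GPG score at Week 16 with a constant p=0.10". Neither section gives an untreated response rate at Week 16, a statement that the infliximab trial measured response on the GPG scale or an equivalent, or a sensitivity analysis over other null values.

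Concomitant Treatment adds that "Concomitant medications are permitted for the treatment of stable, chronic illness as well as for pyoderma gangrenosum".

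**The concern.** In a single-arm trial the null stands in for the missing control group. Rejecting it speaks to a drug effect only if it is at least as high as the response rate these patients would have shown without the drug. Here the null comes from a reading at Week 2, while the endpoint is read at Week 16. That leaves 14 further weeks for change, with other treatment for the disease allowed. The source is also small, so its own uncertainty reaches well above 10%.

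What is at stake is the conclusion drawn from a modest result. With 6 to 10 responders of 20, the plan as written would report that 10% has been rejected at 2.5%, in a trial whose stated purpose is to demonstrate efficacy.

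**Working it through.** **Inputs.** From Sample Size: n = 20, null p0 = 0.10, one-sided 2.5% binomial test, 36.6%, 81% power, 6% of 17 patients at Week 2. From Endpoints and Analysis of Primary Endpoint: response is a fall of one GPG point at Week 16, tested against 0.10. The no-drug rates of 15 to 30% below are assumptions, because the documents give none.

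**1. The plan's own test.** With X the number of responders, P(X ≥ r | 20, p) = Σ from k = r to 20 of C(20,k) p^k (1−p)^(20−k).

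- P(X ≥ 5 | 20, 0.10) = 0.0432, above 0.025.
- P(X ≥ 6 | 20, 0.10) = 0.0113, below 0.025.

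So the rule is 6 of 20 or more, with exact error 1.1%. Its power is 79.9% at a response rate of 36.6%, close to the stated 81%. If 36.6% is instead a difference from 10% (a rate of 46.6%), the power is 95.9%. The argument below does not depend on which was meant.

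**2. The source of the null.** 1/17 = 5.9%, which rounds to 6%, so one responder is inferred. The Clopper-Pearson 95% limits are:

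- lower: 1 − 0.975^(1/17) = 0.15%;
- upper: the p that solves (1−p)^17 + 17p(1−p)^16 = 0.025, which is 28.7%.

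The upper limit of the 90% interval is 25.0%. These limits describe Week 2 only. They make no allowance for change between Week 2 and Week 16, or for a different response definition.

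**3. How far the 2.5% holds.** Solving P(X ≥ 6 | 20, p) = 0.025 gives p = 11.9%. Setting the null at 10% and not 6%, together with the discreteness of the test, therefore protects against a true no-drug rate up to 11.9% and no further.

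**4. Above that rate, and the counts that exclude it.**

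| No-drug Week 16 rate | Chance of 6 or more of 20 | Count that excludes this rate at one-sided 2.5% | Exact error at that count | Power of that count at a 36.6% response |
|---|---|---|---|---|
| 10% (the plan) | 1.1% | 6 | 1.1% | 80% |
| 15% (assumed) | 6.7% | 7 | 2.2% | 64% |
| 20% (assumed) | 19.6% | 9 | 1.0% | 29% |
| 25% (assumed) | 38.3% | 10 | 1.4% | 16% |
| 30% (assumed) | 58.4% | 11 | 1.7% | 7% |

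The first three assumed rates lie inside the 95% interval for 1/17. The fourth lies just above it.

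**The case against.** The strongest reply is that the plan claims no more than it can deliver. The 2.5% is attached to a test against a stated constant, and that test is conservative. The trial calls itself proof-of-concept, an external benchmark is unavoidable in a single arm, and 10% was set above the observed 6%. This stands as far as the test goes: a reader might infer that the test is invalid or its error miscalculated, and neither is so. It does not cover the stated aim of demonstrating efficacy, which needs the further step from exceeding 10% to an effect of the drug.

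A second reply is that some provisions argue for a low no-drug rate. Concomitant Treatment says that other treatment for the disease is to be tapered where tolerated, and Inclusion Criterion 5 requires a lesion that has already failed a therapy. Both stand. They bear on the rate in the opposite direction from the longer time to assessment and the permitted background treatment. The documents do not give the figure that would settle the balance.

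Two stronger readings are tempting:

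- **That the trial's real false-positive rate is 20% or 58%.** Those values follow from assumed rates and are not estimates.
- **That scoring noise and selection on a GPG score of 3 or more must push spontaneous response above 10%.** Under Appendix 1, a subject entering at a sum of 16 or 21 does drop a band with a fall of one point. But a subject entering at 20 needs 5 points and one at 26 needs 6. The documents give neither the scoring error nor the distribution of entry scores. Procedures also strongly recommends the same assessor throughout.

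**Conclusion.** The concern holds as a limit on what may be concluded. The test against 10% is sound. The evidence offered for 10% is a 6% response in 17 patients, 14 weeks earlier in the course than the endpoint and on a response definition that the documents do not match to GPG. The error for a drug effect is at most 2.5% only if the no-drug Week 16 rate is no higher than 11.9%, and the documents contain nothing that establishes this. If the rate were 15%, the error would be 6.7%; if 20%, 19.6%.

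The result rests on 20 evaluated subjects, the one-sided 2.5% level from Sample Size, and the inference that 6% of 17 means one patient.

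A reader might also infer that the null must be raised, or that efficacy may be claimed only once 25% is excluded. The documents do not support either. They single out no higher rate, and the 25% bar would need 10 of 20, with 16% power at a 36.6% response.

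**What to change.** Keep the sample size, the endpoint, its reference to baseline and the test against 10%. Make two changes:

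1. In Sample Size and in Analysis of Primary Endpoint, state that rejection shows that the Week 16 response rate exceeds a fixed 10% benchmark drawn from Week 2 placebo data, and that it does not establish efficacy at a 2.5% error. Bring the sentence on the trial's purpose into line.
2. Pre-specify a sensitivity table at one-sided 2.5%. With 20 subjects, 6 responders exclude 10%, 7 or 8 exclude 15%, 9 exclude 20%, 10 exclude 25%, and 11 or more exclude 30%. Recompute the counts if fewer than 20 are evaluated, since the Study Design Overview allows up to 20.

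This needs wording and one table, with no new data, visits or subjects. The cost is a weaker claim when 6 to 10 of 20 respond. The report would then say which background rates the result excludes and which it leaves open.

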Trained assessors will perform clinical assessments. It is strongly recommended that the same assessor/s perform clinical assessments for a subject at all study visits. The following procedures will be performed at each visit:

Screening

Visit 1 – Screening (within 4 weeks of Baseline)*

- Obtain signed IRB-approved informed consent and HIPPA agreement
- Review Inclusion and Exclusion Criteria
- Review PARACELSUS Criteria and confirm the PARACELSUS score for patient and target lesion is greater than or equal to 10
- Record gender, race, ethnicity, and medical history
- Review personal and family history of PG, inflammatory bowel disease, rheumatoid arthritis, hematological, and autoimmune diseases as well as personal lifetime surgical history
- Perform limited physical exam and vitals, including blood pressure and heart rate
- Record all concomitant medications as well as all those received within the three months prior to screening; assess adverse events.
- PG history assessment (date of onset for each PG lesion) extracted from electronic medical records or obtained from referring provider
- Record all prior topical, systemic therapies/treatments or interventional treatment for pyoderma gangrenosum
- Serum HCG for all female subjects of child-bearing potential to confirm subject is not pregnant.
- Complete blood count (CBC) with differential, Comprehensive metabolic panel (CMP), C-reactive protein (CRP), QuantiFERON-TB Gold test or PPD, HIV, Hepatitis B (Core, Surface Antigen, Surface Antibody), Hepatitis C Antibody.
- PG clinical assessments (including number/location/measurements of PG lesions, GPG score for target lesion)

*If more than 28 days has lapsed between screening and Baseline/Visit 2, then all procedures should be repeated except for re-obtaining informed consent.

Baseline

Visit 2 – Baseline (Week 0)

- Confirm all inclusion and exclusion criteria have been met
- Record concomitant medications (including use of pain medication) and adverse events
- Patient Pyoderma Gangrenosum Questionnaires and DLQI
- Obtain vital signs

- Perform limited physical exam
- Standardized clinical photography of target lesion and other PG lesions
- PG clinical assessments (including number/location/measurements of PG lesions, GPG score of target lesion)
- Assess status of associated co-morbidities such as IBD or RA. Categorize co-morbid condition status as “improved, no change, worsening”.

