- An infection that requires systemic treatment with antibiotic, antifungal, antiviral, anti-parasitic, or anti-protozoal agents or requires oral treatment with such agents for longer than 2 weeks. Treatment of certain infections such as latent tuberculosis may be treated concurrently with spesolimab treatment

Duration of study drug suspension should be reviewed on a case-by-case basis and can be discussed with the PI.

In case of systemic hypersensitivity including infusion reactions and anaphylactic reaction, emerging during or after infusion/injection of study medication, the investigator should consider in accordance with severity of the reaction and local standard of care to:

- Immediately interrupt the infusion/injection

- Treat with systemic anti-histamines, intravenous steroids, and in case of a severe allergic reaction (e.g., anaphylactic reaction) epinephrine
- Blood draw for plasma sample of IgE and ADA/neutralizing antibody (Nab), serum tryptase, and complement components

In case of systemic hypersensitivity including infusion reactions, based on patient's clinical course and medical judgment, the infusion may be re-initiated in case of mild or moderate infusion reactions at lower speed with gradual increase to complete the infusion as detailed in the label. Regardless, the total duration of infusion should not exceed 180 minutes (3 hours).

Safety Evaluation

This is an open label, proof-of-concept study with an FDA-approved drug. Safety and tolerability will be evaluated from the AEs, limited physical examinations, and vital sign measurements. More frequent safety evaluations may be performed if clinically indicated or at the discretion of the investigator.

Aggregated AEs will be evaluated monthly by the PI/research teams.

Safety data will be reviewed by the investigators who will monitor the study on a regular basis and meet regularly (approximately once a month, depending on the number of subjects enrolled). The local IRBs, FDA, and Boehringer Ingelheim will be notified of adverse events (as required by each institution).

Physical Examination/Vital Signs

Qualified personnel will perform limited physical examinations, blood pressure and heart rate at each visit.

Limited physical examination consists of assessments of general appearance; skin; head, eyes, ears, nose, and throat (HEENT); heart; lungs; abdomen; extremities; neurological function; and lymph nodes.

MEASURES TO MINIMIZE/AVOID BIAS:

Subject Identification

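### The plan does not conceal subject, visit or date from whoever measures lesion area in ImageJ, although stored photographs would allow it cheaply

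*Combined protocol and SAP*

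**What the plan says.** The *Study Design Overview* is explicit about the design: "This study is a prospective, proof-of-concept, open label clinical trial". There is one treatment group.

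Lesion size is obtained in two ways, both described under *Target Lesion Measurement and Digital Image Assessments*. The first is a bedside measurement: "Size of target PG lesion will be approximated at each visit by measuring the length, width and depth of the lesion". The second is image-based: "Target lesion will also be analyzed using Image J software to obtain a more precise surface area of each lesion". The images come from the photography listed in *Procedures*: "Standardized clinical photography of target lesion and other PG lesions".

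The *Interim Analysis* section, which applies once the first 10 subjects have completed Week 16, adds: "Changes from baseline at Week 16 in the PG lesions (number, size, GPG score) will be evaluated and reported". It does not say which of the two measurements supplies size.

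The section headed "MEASURES TO MINIMIZE/AVOID BIAS" has one subsection, on subject identification. It opens with "Subjects are numbered sequentially" and goes on to screening numbers, the master log and privacy. On assessors, *Procedures* asks for training and says "It is strongly recommended that the same assessor/s perform clinical assessments for a subject at all study visits".

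**The concern.** An area measured from a photograph depends on where the ulcer edge is taken to lie. In a healing ulcer part of that edge can be ambiguous. A reader who knows that an image is from Baseline, or from Week 16 on active treatment, may settle the ambiguity in the direction expected. With no concurrent control, such a difference between visits cannot be separated from healing.

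Stored photographs are well suited to concealed reading, because the person who measures them need not have been at the visit and need not know when the image was taken. The plan takes the photographs and intends to measure them, but does not use this opportunity. At stake is the credibility of a supportive size result, notably in an interim report on 10 subjects. The primary result is not at stake.

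**Working it through.** **Step 1. What is specified about the image reading.**

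| Question | What the documents say |
|---|---|
| Is treatment open? | Yes (*Study Design Overview*) |
| Who reads the images? | Not stated |
| In what order are they read? | Not stated |
| Are subject, visit and date hidden? | Not stated |
| Does the bias section address it? | No; it covers numbering, the log and privacy |
| Do the assessor provisions address it? | No; training, a consistent assessor and standardized photography improve consistency but conceal nothing |

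Some pages were not available for this review, so these statements cover the text that was.

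**Step 2. Where the area could be used.** *Endpoints* lists no area measure. *Statistical Considerations* gives area no test, interval or summary. The only reported analysis that names lesion size is the interim one. There the source could be the ruler, or it could be ImageJ, which the plan describes as the more precise of the two. The GPG score has a diameter item (*Appendix 1*), but nothing ties that item to ImageJ.

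**Step 3. Sensitivity of area to edge placement.** The plan gives no repeatability or reading-error figure, so there is nothing of its own to reproduce. Its sample-size statement concerns GPG success only, and area does not enter it. The following is therefore an illustration under stated assumptions: a round ulcer of diameter d, with the edge moved inward by the same distance s all the way round. The diameters 2, 4, 6 and 10 cm are cut-points of the GPG size item.

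Area is proportional to the square of the diameter, so

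share of area removed = 1 − ((d − 2s)/d)²

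| d | s = 1 mm | s = 2 mm |
|---|---|---|
| 20 mm | 1 − (18/20)² = 19.0% | 1 − (16/20)² = 36.0% |
| 40 mm | 1 − (38/40)² = 9.8% | 1 − (36/40)² = 19.0% |
| 60 mm | 1 − (58/60)² = 6.6% | 1 − (56/60)² = 12.9% |
| 100 mm | 1 − (98/100)² = 4.0% | 1 − (96/100)² = 7.8% |

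**Step 4. What this means for change from baseline.** Take an ulcer of 4 cm that has not changed. If its edge is placed correctly at Baseline and 1 mm inward at Week 16, it shows a 9.8% reduction with no healing. If the edge is 1 mm inward at both visits, the ratio of the two areas is (38/40)² ÷ (38/40)² = 1 and no change appears. For an unchanged ulcer, then, what matters is a shift that differs by visit. Hiding the visit and mixing the reading order acts on exactly that. The same shift also takes a larger share of a smaller ulcer, so the measure is most sensitive as lesions heal.

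**The case against.** Much of the case on the other side stands and limits the point.

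- A reader might infer that the photographs are traced unmasked, or analysed visit by visit. The documents do not say so. The reference to each visit describes when photographs are taken, not when or in what order they are read; the plan also does not say that the edge is placed by hand. The supportable statement is that concealment and reading order are not specified.
- A reader might infer that area is the only outcome that can be assessed without knowing the visit. It is not. Cytokines, CRP, pharmacokinetics and antibodies can be assayed without that knowledge, and several GPG items (border erythema, percentage of active ulcer, granulation, diameter) could be graded at least partly from coded photographs.
- A reader might infer that a smaller traced area at Week 16 signals bias. Leaving out skin that has truly re-epithelialised is correct reading. Bias arises only if ambiguous or open ulcer is left out because of what the reader expects.
- Interim size may well be the ruler measurement. The same part of the plan introduces size through length, width and depth, and the interim wording resembles the list of bedside assessments. This is a fair reading but not a stated one. The interim section gives no stopping rule and enrolment continues, so no stated decision depends on area.
- The 1 to 2 mm shift is assumed, uniform and in one direction. The arithmetic shows sensitivity, not a likely error in this trial.
- Unmasked bedside grading of GPG matters more, since GPG is the primary endpoint. That is true, but purulence on gauze and depth need examination in person, so GPG cannot be fully masked. Image area can be handled more easily.

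**Conclusion.** The point holds as a modest, inexpensive improvement. In an open-label trial without a control group, the plan commits to an image-based area and to an interim report of lesion size, and specifies no concealment of subject, visit or date from the image reader.

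The possible effect runs from about 4% of area (1 mm, 10 cm ulcer) to 36% (2 mm, 2 cm ulcer). That range rests wholly on the assumed shift and a round shape. Whether any such shift would occur is unknown. The relevance to the interim also depends on size being taken from ImageJ, which the plan leaves open.

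It would be wrong to conclude that the primary result is threatened. The primary test uses the GPG score, area is neither a primary nor a secondary endpoint, and the documents do not feed ImageJ output into GPG.

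**What to change.** Add a paragraph to *Target Lesion Measurement and Digital Image Assessments* with these elements:

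1. Before ImageJ reading, target-lesion photographs are exported under random codes, with subject, visit and date removed.
2. Whoever on the existing team does the ImageJ reading takes them in random order across subjects and visits.
3. There is one batch for the interim and one for the final analysis. The code for a batch is broken only after its areas are locked.

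In *Interim Analysis*, state whether size means the ImageJ area or the ruler measurement.

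The cost is one paragraph, a sentence and some file renaming. No visit or patient burden is added, and no extra reader is needed if a member of the existing team reads the images. The drawbacks are that areas become available in batches rather than as visits occur, and that masking is imperfect, because healing is visible and staff at a single site may recognise individual lesions. Random order still removes certain knowledge of the visit.
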